9.2.2 Handling of Intercurrent Events of Primary Estimand(s)

Intercurrent events are: progression of osteoarthritis up to TKA, lost to follow up, premature death, the patient wishes to change to the operated group after a certain time. (as stated under point 3).

Data obtained until the event will be included in the analysis, last observation will be included in the evaluation. In case of progression of osteoarthritis up to TKA the procedure will be noted as fail. Premature death will be treated as lost to follow-up. Lost to follow-up and premature death can be unrelated to knee problems. If the patient wishes to change the treatment group, data are collected for this treatment up to the last treatment. If more than 20 % of patients fail, the benefit-risk balance will be re-evaluated, and it will be decided if the trial will be continued.

9.2.3 Handling of Missing Data

If the patient withdraws his consent, data up to this date will be used for the analysis. The last observation carried out will be the end point. Patient will be reported as withdrawn.

Patients are not randomized and do not have therapy after surgery, they just have follow-up visits. There will be the full analysis set model for the analysis, thus all data from patients will be reported, which were

enrolled. If a patient is lost to follow up, the patient will be reported as this.

For patients with progressing of osteoarthritis up to TKA, they will be recorded as failed. Data up to the event will be analyzed.

There will be no assumptions made for missing data. Data from last observation will be analysed. A drop-out of 20% is accepted in orthopedic trials.

9.2.4 Sensitivity Analysis

The intercurrent events in this trial are progression of osteoarthritis up to TKA, lost to follow-up, premature death and change to the other treatment group. Progression of osteoarthritis up to TKA will be defined as procedure failure. Lost to follow-up and premature death can be unrelated to knee problems. Both will be defined as lost to follow up. Lost to follow-up will reduce the power of the result. A drop-out of 20 % is acceptable and will not bias the result.

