9.2.1 Statistical Model, Hypothesis, and Method of Analysis

The change in PROMS from baseline in the operated and non-operated group will be compared by two-sided t-test for independent groups when data are normally distributed or with the Mann-Whitney-U-test.

The Null-hypothesis is that partial meniscal replacement does not improve mean PROMs for knee function in comparison to the non-operated group after 2 and 5 years.

The alternative hypothesis is that there that partial meniscal replacement does improve mean PROMs for knee function in comparison to the non-operated group after 2 and 5 years.

The PROMS should improve (Mean KOOS and IKDC should increase by at least 20 points, and VAS-pain score should decrease by at least 3 points, or to near zero, depending on the pre-surgical value).

Analysis of data will be performed by direct comparison of the groups at each time point and in comparison, to before surgery/start of the trial. Mean and standard deviation of the groups are compared. If there is a significant difference, the Null-Hypothesis will be rejected. Even when we have a loss of follow-up of 20% the power will still be 0.985. From our experience mean KOOS values presurgical are between 40-50 and between 50-60 for the IKDC, after treatment the expected improvement is to mean values between 80-90 for both scores. For the VAS-pain-score the presurgical mean value is around 4 and the post-surgical value is between 0 and 1. There is no risk of a type 1 error, because the values are measured several times over the follow-up period, thus there will be no false positive result. If the difference in the scores between pre- and post-surgery is lower than 18, the power is not big enough. Thus setting 20 as the difference for rejecting the Null-hypothesis is supported by enough power, even with only 8/24 patients in the respective group. The covariate could be smoking and sex. Smoking affects healing in general. It is not clear if there will be enough patients in each group to use these as confounders. Interactions will not be possible, because the treatment has no relation to any characteristic of the patient. There will be no adjustment made and no model fitting.

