9.3 Analysis Supporting Secondary Objective(s)

Secondary objectives are:

Safety of the patient, efficacy of the procedure, MRI image description and patient satisfaction.

Patient safety will be analyzing the number of AE, SAE and SUSARs and will be compared for both groups. The numbers obtained will be compared in a Chi-Square test. SUSARs will only occur, if any, in the operated group and thus cannot be compared to any other value. For categorial variables. Efficacy of the procedure will be analyzed by counting the number of failed procedures in the operated group. Because this value will only be determined in the operated group, there is no statistical analysis. The efficacy of the procedure must be over 80%. If the failed procedures are higher than 20 % the benefit-risk balance will be re-evaluated. The MRI signal will be evaluated after a modified scheme of Genovese [32]. The size of the meniscus and the amount of extrusion of the meniscus will be measured and recorded in both groups. The obtained numbers will be compared to the other group at the same time point and to the value before surgery/at the beginning of the trial. This will be performed with an unpaired t-Test if the values are normally distributed or with the Mann-Whitney-U-test for not normally distributed values. Patient satisfaction is a categorial value and will be only evaluated in the operated group. The number of patients who are very pleased, pleased, not pleased, very unsatisfied will be described by means of frequency tables and plots.

Intercurrent event are: progression of osteoarthritis up to TKA, lost to follow-up, premature death, the patient wishes to change to the operated group after a certain time. If these events happen, the data will be available until the event. Last date recorded will be analyzed. Progression of osteoarthritis up to TKA will be recorded as fail and will be reported as this. Patients changing to the operated group will be analyzed up to the date of change in the non-operated group. Missing data will not be estimated. A drop-out rate (lost to follow-up, premature death) of 20% is expected and accepted.

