9.8 Sample Size Determination

The unpaired t-Test will be used for normally distributed PROMs. Values for the primary outcome are expected to be about 55/84 for the IKDC score and 46/86 for the KOOS pre/postsurgery, respectively. For this calculation, the program G-power was used. A sample size of 9 in the operated group and 3 in the non-operated group would be sufficient to reach a power of 0.982. When we include 10 non-operated patients and 30 operated patients the effect size is 2.0, $\alpha = 0.00655$ and the power is than 0.993. If we have a 20% lost to follow-up, the numbers of patients will be 8/24 and $\alpha = 0.014$ and the power will be 0.985. The number of 30/10 is sufficient to reach a power of >0.8.

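### The protocol says 20% drop-out cannot bias the result and that missing data need no assumption; both statements are wrong, and the missing-data handling is inconsistent

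*Protocol*

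**What the plan says.** Section 9.2.4 treats drop-out as a matter of power only. It states "Lost to follow-up will reduce the power of the result" and then "A drop-out of 20 % is acceptable and will not bias the result". The only reason given is that loss to follow-up and death may have nothing to do with the knee.

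Section 9.2.3 states "There will be no assumptions made for missing data. Data from last observation will be analysed". In its paragraph on withdrawal of consent it adds "The last observation carried out will be the end point". Section 9.2.2 applies a similar rule to progression to TKA, loss to follow-up, death and change of group: "Data obtained until the event will be included in the analysis, last observation will be included in the evaluation".

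Two other places point elsewhere. Section 9.3, on the secondary objectives, says "Missing data will not be estimated". Section 9.2.1 says "Even when we have a loss of follow-up of 20% the power will still be 0.985", and Section 9.8 shows that this figure is computed on 8 non-operated and 24 operated patients, so patients lost to follow-up are not counted.

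**The concern.** The primary endpoint is PROM change at 2 and 5 years. Loss leaves the comparison unbiased only if the values used for lost patients are right on average or, where those patients are omitted, if they resemble the patients who stay. The protocol does not secure either condition:

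- Patients choose their group and nothing is blinded (Section 4.1).
- The investigator may withdraw patients who do not follow the post-surgical restrictions (Section 7.2). Only operated patients can leave this way, and poor adherence may well go with a poor outcome.
- TKA ends follow-up and a change of group ends the data for the first group (Section 7.1.1). Both plausibly relate to the state of the knee.
- Section 11.1 concedes that drop-out above 20% could have a significant impact on the results. Nothing makes 20% the point at which bias begins.

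Using the last observation is itself an assumption, namely that the score stays where it was. PROMs are first repeated at 6 months (Section 9), so a patient lost before then has only the baseline value, and carrying it forward records no change. Because the text supports both carrying forward and dropping lost patients, the data set to be tested is not fixed, and the investigator alone sees and analyses the data while the trial runs (Section 9.7).

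**Working it through.** **1. The plan's own figure.** Section 9.8 gives effect size 2.0, groups of 8 and 24, alpha 0.014 and power 0.985. The noncentral t calculation for a two-sided test has noncentrality 2.0 × √(8 × 24 / 32) = 2.0 × √6 = 4.90 on 30 degrees of freedom, and gives power 0.9857. The stated figure reproduces. It measures precision with 32 patients and says nothing about whether those 32 represent the 40 enrolled.

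**2. Inputs for the bias illustration.**
- Section 9.8: "Values for the primary outcome are expected to be about 55/84 for the IKDC score and 46/86 for the KOOS pre/postsurgery, respectively". Expected gains: KOOS 86 − 46 = 40; IKDC 84 − 55 = 29.
- Section 9.2.1: VAS from about 4 to between 0 and 1, a fall of 3 to 4 (midpoint 3.5).
- 20% loss: 6 of 30 operated patients.
- Assumption for illustration: the lost operated patients are misstated by the whole expected gain, and the non-operated group carries no error.

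**3. Formula.** Shift in the operated mean = share lost × (mean value used − mean true value).

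| PROM | 20% lost | 10% lost |
|---|---|---|
| KOOS | 0.20 × 40 = 8.0 | 4.0 |
| IKDC | 0.20 × 29 = 5.8 | 2.9 |
| VAS | 0.20 × 3.5 = 0.7 (0.6 to 0.8) | 0.35 |

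The wider pre- and post-surgical ranges in Section 9.2.1 give KOOS gains of 30 to 50 and IKDC gains of 20 to 40. At 20% loss the shifts are then 6 to 10 and 4 to 8 points.

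**4. Direction.** If good early scores are carried forward, or the lost patients are simply omitted, while their true scores are back at baseline, the operated mean is overstated. If patients are lost before the 6-month PROM and baseline is carried forward although they did well, it is understated. A simulation with 6 of 30 and 2 of 10 lost gave +8.0 and −8.0 KOOS points for the two carry-forward cases.

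**5. Against the 20-point criterion in Section 9.2.1.**
- At the expected gains, with 6 of 30 set to no change: KOOS 0.8 × 40 = 32; IKDC 0.8 × 29 = 23.2. Both remain above 20.
- At a smaller gain: if 24 observed patients show a mean of 20 to 25 and the 6 lost have none, the mean over all 30 is 0.8 × 20 = 16 to 0.8 × 25 = 20.

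**6. Standard error under carry-forward.** If values are carried for all 30 and 10, add no information, and SDs are equal, the ratio of the standard error used to that from 24 and 8 is √(1/30 + 1/10) / √(1/24 + 1/8) = 0.365 / 0.408 = 0.894, about 11% too small. This does not apply if lost patients are left out.

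**The case against.** The strongest reply has five parts.

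- **Carry-forward is never named.** The sentence making the last observation the end point stands in the paragraph on consent withdrawal, Section 9.3 rejects estimation, and the power count is 24 and 8. This stands. Carry-forward is the natural reading of 9.2.2 and 9.2.3, but the firm charge is inconsistency, and the standard-error result is conditional on that reading.
- **The illustration is extreme and one-armed.** It takes the whole gain from every lost operated patient and ignores errors in the non-operated group, which may offset or add. Section 11.1 also expects loss to follow-up below 10%. This stands, so the shift is an illustration and the 10% column belongs beside it.
- **The target is still met at the expected gains.** This is correct. The issue matters if the real gain is nearer to 20 points.
- **Section 4.2 says remodelling is normally finished by 2 years.** That lends some support to carrying a 2-year score to 5 years, but less to carrying a 6- or 12-month score to 2 years. Either way it is an assumption.
- **Sensitivity analyses may be in a statistical analysis plan.** That is fair, so the absence of one in Section 9.2.4 is not itself the point. The point is what the protocol states.

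A reader might infer that 8 points is the most the PROM effect can move, or that the 5-year result would consist largely of 12- or 24-month scores. Neither is supported. Eight points is a KOOS scenario: other inputs give more or less, and a shift of that size is impossible on the 0 to 10 VAS at 20% loss. At 20% loss, 24 of 30 operated values would still be genuine 5-year scores.

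**Conclusion.** Two statements in the protocol are wrong as written: that 20% drop-out cannot bias the result, and that using the last observation involves no assumption. The missing-data handling is also not consistent across Sections 9.2.1, 9.2.2, 9.2.3, 9.3 and 9.8.

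At 20% loss, with lost operated patients misstated by the full expected gain and no error in the other group, the size is about 8 KOOS, 5.8 IKDC or 0.7 VAS points in either direction. At 10% loss it is about half. The shift is zero only if the values used are right on average. The documents do not support a claim that drop-out would overturn the planned conclusion, because the expected gains leave room. They do support the claim that a gain near the 20-point criterion could be misjudged while the protocol's text says that no bias is possible.

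**What to change.** - Delete from 9.2.4 the statement that drop-out will not bias the result, and from 9.2.3 the statement that no assumptions are made. Say instead what is assumed about lost patients.
- Fix one rule for the 24-month and 5-year analyses that uses PROMs observed at those visits and not the last observation. Reconcile Sections 9.2.2, 9.2.3, 9.3 and 9.8 with it, including how patients whose data end at TKA or at a change of group enter the comparison. A repeated-measures model is an option only if Section 9.2.1, which rules out fitting a model, is amended.
- Observed cases alone do not remove the bias: omitting six patients without lasting gain gives the same 8-point KOOS overstatement. Add one sensitivity analysis that sets missing operated patients to no change from baseline, and report whether the conclusion holds.
- For patients who stop attending but have not withdrawn consent, collect KOOS, IKDC and VAS by post or telephone at 24 months and 5 years. Patients complete the forms without the investigator's help (Section 4.1), so this is feasible.

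The cost is protocol wording, one extra analysis, a few mailed forms and possibly a less favourable result.

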9.2.5 Supplementary Analysis

Age, sex, and smoking may be subgroups. If there are enough patients for subgroups they will be analyzed.

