5.2 Rationale for Trial Population

The rational for choosing this trial population is that this part of the population has this kind of diagnosis, and it must be treated as soon as possible. Additional measures are taken for leg axis misalignment and ACL rupture. For the efficacy of the procedure the leg must have a normal alignment and must be stable.

No children or patients, who are unable to consent for themselves, or those that may respond to the trial intervention differently are included. There is no restriction on medicine taken by the patient because the allograft does not have systemic actions.

Screening is performed via MRI. There must be a sufficient standing peripheral rim, so that the procedure can be performed. No laboratory tests or genetic tests are necessary for the screening. When the operation is decided later on, the usual laboratory tests are performed as for every surgery, not being a trial. Only after successful screening the patient will be enrolled. Subgroup possible will be sex (female versus male) and smoker versus non-smoker if enough power is generated to do statistical calculations.

Individuals who do not meet criteria for trial eligibility will not be enrolled via protocol waivers. or exemptions.

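### Subgroup analyses hang on an undefined condition while interactions are ruled out on a false argument, which leaves separate within-subgroup tests that can mislead

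*Protocol*

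**What the plan says.** Three sections bear on subgroups.

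- Protocol 9.2.5, which names age, sex and smoking as possible subgroups: "If there are enough patients for subgroups they will be analyzed".
- Protocol 5.2: "Subgroup possible will be sex (female versus male) and smoker versus non-smoker if enough power is generated to do statistical calculations".
- Protocol 9.2.1, in the discussion of covariates: "Interactions will not be possible, because the treatment has no relation to any characteristic of the patient". The same paragraph says that smoking affects healing, doubts that there will be enough patients to use smoking and sex as confounders, and excludes adjustment and model fitting.

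Section 9.2 gives p < 0.05 as the criterion for significance, and 9.2.1 names the two-sided t-test for independent groups or the Mann-Whitney U test. Section 9.8 plans 30 operated and 10 non-operated patients (24 and 8 after 20% loss) at an effect size of 2.0. It also says, about the trial as a whole: "A sample size of 9 in the operated group and 3 in the non-operated group would be sufficient to reach a power of 0.982".

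**The concern.** The two lists differ, since age appears only in 9.2.5. The two conditions also differ (patients in one, power in the other), and neither has a number. Whether a subgroup qualifies would therefore be decided after enrolment. Under 4.1 and 9.7 that decision falls to the unblinded investigator, who also runs the analysis.

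The larger problem is the reason given in 9.2.1. Whether the effect of surgery varies with sex, age or smoking is an empirical question. If the sentence means that treatment choice is unrelated to patient characteristics, that has no bearing on effect modification, and in a trial where patients choose their group it is not assured. If it means that the effect is the same in everyone, it is asserted without evidence, sits badly with the remark on smoking and healing, and would leave subgroup analyses without a purpose.

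With interactions excluded, the comparison the text leaves is one test per subgroup. A finding in non-smokers but not in smokers would then largely reflect how many of the 10 controls fell in each cell. The stake is a published statement about who benefits that the data cannot support.

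**Working it through.** **Inputs.** From 9.8: 30/10, 24/8 and 9/3 patients, effect size d = 2.0 (in SD units; no SD is given). From 9.2 and 9.2.1: two-sided t-test, p < 0.05. Subgroup prevalences are not in the protocol. I assume two factors at 50:50 (sex, and age at some cut-off) and one at 25% (smoking).

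**1. The protocol's own power figures.** Power = P(T > t₁₋α/₂) for noncentral t with n₁ + n₀ − 2 degrees of freedom and noncentrality d·√(n₁n₀/(n₁+n₀)).

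| Operated/non-operated | Noncentrality at d = 2.0 | α | Power stated | Power computed |
|---|---|---|---|---|
| 30/10 | 2√(300/40) = 5.48 | 0.00655 | 0.993 | 0.9935 |
| 24/8 | 2√(192/32) = 4.90 | 0.014 | 0.985 | 0.986 |
| 9/3 | 2√(27/12) = 3.00 | 0.05 (none stated) | 0.982 | 0.77 |

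The first two reproduce. The third does not: 0.982 with 9/3 needs d of about 3.0 at two-sided 0.05. So 9/3 is a permissive yardstick for a subgroup.

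**2. How often both levels of a factor reach 9/3.** This is the exact binomial probability that both levels hold at least 9 operated and at least 3 non-operated patients.

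| Share in the smaller level | 30/10 | 24/8 |
|---|---|---|
| 50% | 0.88 | 0.60 |
| 40% | 0.74 | 0.42 |
| 30% | 0.35 | 0.12 |
| 25% | 0.155 | 0.04 |
| 20% | 0.04 | 0.01 |

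For two 50% factors and one 25% factor, taken as independent, at least one qualifies with probability 1 − (1 − 0.876)² × (1 − 0.155) = 0.987 at 30/10 and 0.85 at 24/8.

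**3. Why separate tests disagree under one common effect.** At d = 1.5, power is 0.91 in a 21/7 subgroup and 0.53 in a 9/3 subgroup. The chance that exactly one is significant is 0.91 × 0.47 + 0.09 × 0.53 = 0.48. At d = 2.0 the powers are 0.993 and 0.771, giving 0.993 × 0.229 + 0.007 × 0.771 = 0.23. In an even split (15/5 twice, power 0.955) it is 2 × 0.955 × 0.045 = 0.09.

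**4. All three factors together.** I simulated one normal outcome with the same effect d in everyone and factors independent of outcome and group. Any stratum with at least 9 operated and 3 controls was tested by pooled t-test at 0.05. The entries are the share of trials in which at least one factor is significant in one level and not in the other.

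| d | 30/10 | 24/8 |
|---|---|---|
| 2.0 (protocol) | 0.19 | 0.22 |
| 1.5 (sensitivity) | 0.50 | 0.44 |
| 1.0 (sensitivity) | 0.64 | 0.46 |

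For a single 50:50 factor at 30/10 with both levels qualifying, the figures are about 0.12, 0.38 and 0.51. A direct test of the treatment-by-subgroup difference flags about 5% throughout.

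**5. What the valid contrast can deliver.** With 15/5 in each level, its SE is √(1/15 + 1/5 + 1/15 + 1/5) = 0.73 SD, against √(1/30 + 1/10) = 0.365 SD for the whole-trial difference. For 80% power the effects would have to differ by about (1.96 + 0.84) × 0.73 ≈ 2.05 SD.

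**The case against.** Section 9.2.5 is a supplementary analysis, says only that these factors may be subgroups, and names no test. The sentence on interactions stands in the covariate discussion of the primary comparison. No objective, endpoint or stopping rule depends on a subgroup. Minimum cell size and exploratory labelling are often left to a statistical analysis plan, which may exist. All this is fair, and missing detail alone would not be a finding. What stands is that the protocol itself names two different lists and excludes the one valid comparison for a wrong reason.

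Three stronger readings are tempting, and the documents do not support them.

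- A reader might infer that 9/3 is the trigger and that almost every split meets it. Section 9.8 gives 9/3 for the whole trial, and neither subgroup section refers to it. Section 9.2.1 speaks of 8/24 patients, and 9.8 also uses power above 0.8. Even under 9/3, both levels of a 25% smoking factor qualify in only about 16% of trials at 30/10 and 4% at 24/8.
- A reader might set a 59% chance of some false positive subgroup result against a nominal 5%. That figure assumes three PROMs at two times repeated in every stratum. Six whole-trial tests alone give about 21% under the same assumed correlation of 0.5, and that is multiplicity of the primary endpoint, a separate matter. On one outcome the subgroup figure is about 18% (15% at 24/8).
- A reader might conclude that chance differences will look real. At the protocol's d = 2.0 most trials would show no such contrast, so the supported statement is that they can.

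**Conclusion.** The concern holds in this form: an undefined condition judged after enrolment, two inconsistent lists, and a false reason for excluding interactions together leave within-subgroup tests that cannot show a difference in effect. At the protocol's assumed effect the misleading contrast is a moderate risk, about one trial in five. It rises to roughly 45 to 65% if the true effect is 1.0 to 1.5 SD, which the protocol does not assume. These sizes rest on assumed prevalences, on 9/3 as an illustrative rule, on one outcome, and on the reading that p < 0.05 in 9.2 applies within subgroups. The error in the reasoning of 9.2.1 and the mismatch between 5.2 and 9.2.5 need no assumption. The primary comparison is not affected.

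**What to change.** - In 9.2.1, delete the sentence on interactions.
- In 5.2 and 9.2.5, use one list of subgroups, with the age cut-off fixed in advance.
- Replace the conditions on patients and power with a rule such as: subgroup results are exploratory; the operated minus non-operated difference in mean change is shown with its 95% CI per subgroup, without within-subgroup p-values; where a cell falls below a preset minimum size, only descriptive data are shown.
- Add that any statement that the effect differs between subgroups rests only on the treatment-by-subgroup difference with its 95% CI. This is the difference between two subgroup differences, so it needs no change to the primary test.

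The cost is wording in three sections. The investigator gives up significance claims within subgroups. The treatment-by-subgroup estimate will be very imprecise (SE about 0.73 SD even at 15/5 versus 15/5), and the protocol should say so, so that a wide interval is not read as evidence that effects are equal.
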